24.2.4 Vital signs and C-SSRS

Vital signs and C-SSRS assessments will be performed at all DBP and OLEP post-baseline visits except the two Telephone visits (i.e., Visit 4 and Visit 8), and hence only the above narrow windowing will be applied. The C-SSRS will in addition be assessed at the Screening Visit.

24.2.5 Weight

Weight assessments will be performed at the following visits, and hence a broad windowing will only be applied for these visits. A narrow window will also be defined using all perprotocol defined visits as scheduled in Panel 18 above. Weight is not collected in the OLEP.

Nominal Vis Number (DB-Period)	Nominal Vis Week	Nominal Vis Day	Time Window narrow ¹	Time Window broad ¹
V1 (Screening Visit – planned eval)	-6	-42	See Panel 16	NA
V3 (Baseline Visit – planned eval)	0	0		-7 to 7
V9 (planned eval Visit)	12	84		50 to 126
V12 (planned eval Visit)	24	168		127 to 210
V15 (planned eval Visit)	36	252		211 to 294
V18 (planned eval Visit)	48	336		295 to 378
V24 (planned eval EoTDBP/WD Visit)	72	504		463 to 518

Panel 19 Visit Windows for Weight

All post-baseline visits (except EoT visits) can be converted into a Withdrawal (WD) Visit.

¹ For DBP the applied narrow window will be continuous (i.e., ± 14 days) to avoid invalid assessments (protocol text ± 3 days). The broad window is set up to allow additional flexibility.

24.2.6 ECG

ECG assessments will be performed at the following visits, and hence a broad windowing will only be applied for these visits. A narrow window will also be defined using all per-protocol defined visits as scheduled in Panel 18. ECG is not collected in the OLEP.

Nominal Vis Number (DB-Period)	Nominal Vis Week	Nominal Vis Day	Time Window narrow ¹	Time Window broad ¹
V1 (Screening Visit – planned eval)	-6	-42	See Panel 16	NA
V3 (Baseline Visit – planned eval)	0	0		-7 to 7
V6 (planned sampling Visit)	6	42		36 to 49
V12 (planned eval Visit)	24	168		127 to 210
V18 (planned eval Visit)	48	336		295 to 378
V24 (planned eval EoTDBP/WD Visit)	72	504		463 to 518

Panel 20 Visit Windows for ECG

All post-baseline visits (except EoT visits) can be converted into a Withdrawal (WD) Visit. ¹ For DBP the applied narrow window will be continuous (i.e., ± 14 days) to avoid invalid assessments

(protocol text ± 3 days). The broad window is set up to allow additional flexibility.

24.2.7 Fall Diary

Each Fall Diary period will be defined as the period between the two visits where the diary was supposed to be filled out according to the protocol. Hence, even though this per protocol has been defined as a two-week period for the baseline period and a four-week period for the subsequent periods, the length of each individual period will slightly vary depending on the visit structure for each individual patient. Hence, the following rules will be applied for mapping data into the periods:

Period (DB-Period)	Start visit	End visit	Planned duration	window around both visits*
Period 0 (Baseline)	Visit 2 (R. visit)	Visit 3 (BL visit)	2 weeks	+/- 3 days
Period 1 (post-IMP)	Visit 7	Visit 9	4 weeks	+/- 3 days
Period 2 (post-IMP)	Visit 11	Visit 12	4 weeks	+/- 3 days
Period 3 (post-IMP)	Visit 14	Visit 15	4 weeks	+/- 3 days
Period 4 (post-IMP)	Visit 17	Visit 18	4 weeks	+/- 3 days
* Fall Diary data availa	ble within the accepta	able window to be inc	cluded in the period.	

Panel 21 Windows for Fall Diary (Periods)

For each period, the data will be mapped into the end visit. Only one windowing approach will be defined around the relevant visits. The Fall Diary data is not collected in the OLEP.

Visit windows for FeetMe and PAMSys devices will be defined on a similar way for consistency.

24.3 Assigning Adverse Events to Analysis Phases

Adverse events will be assigned to an analysis period as follows:

- Adverse events prior to treatment Records not classified as TEAEs will have APHASE= PRETREAT
- Adverse events in the double-blind period (DBP) all TEAEs with date of onset or worsening of intensity/seriousness after first dose of IMP in the DBP and until first dose of IMP in the OLE period (planned for Visit 1E – for patients entering the OLE) or the Safety Follow up visit for the DBP (SFU Visit 25 – for patients NOT entering the OLE) (assigned APHASE = DOUBLE BLIND).
- Adverse events in the Open-Label Extension period TEAEs with date of onset or worsening of intensity/seriousness after first dose of IMP in the OLE period (Visit 1E) and until the final Safety Follow up visit for the OLE (Visit 64E) (assigned APHASE = OLE).

If the start date is missing/incomplete and not eligible for imputation, the TEAE will be assigned to the DOUBLE BLIND phase.

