## 7.4 Method of Assigning Patients to Treatment

IRT will be used in this study. Each patient will be assigned a screening number by the IRT, and that number will be used to identify the patient throughout the study. When a patient is to be randomized, the investigator or a designated, unblinded site staff will use the IRT. The IRT allocates the patient to a treatment group and assigns the patient a randomization number in accordance with the specifications from Biostatistics, Lundbeck.

Randomization will take place at Visit 2 after confirmation that the participant continues to meet the inclusion/exclusion criteria. Patients will be randomized 2:1 to receive either study drug or placebo.

In the optional OLE period, all patients will receive Lu AF82422.

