#### 17.10 Safety Analyses

#### 17.10.1 Analysis of Adverse Events

Adverse events will be classified according to the time of onset of the adverse event:

- pre-treatment adverse event an adverse event that starts on or after the date the patient signed the *Informed Consent Form* and prior to the date of first dose of IMP
- *treatment-emergent adverse event* an adverse event that starts or increases in intensity during or after administration of first dose of IMP

Adverse events, sorted by system organ class and preferred term, will be summarized by period and treatment group.

Data on adverse events related to systemic hypersensitivity reaction collected via the dedicated *Hypersensitivity Form* will likewise be summarized by period and treatment group.

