24.4.4 Adverse Event Start and Stop Dates

If the start date is missing/incomplete for an adverse event and the stop date is prior to the first dose of IMP, the adverse event will be classified as a pre-treatment adverse event. In all other cases of an adverse event with a missing/incomplete start and/or stop date, the adverse event will be classified as a TEAE. No imputation of start/stop dates will be done, except in the case of adverse events which change in intensity/seriousness. For details on deriving multiple events from change in intensity/seriousness, and corresponding stop- and start dates, see section 24.5.2.

For adverse events ongoing at the end of the study, the date of the last study contact will be used as the stop date for the adverse event in the calculation of duration. For other adverse events with a missing/incomplete start or stop date, the duration will not be calculated.

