24.5.2 Changes in Intensity or Seriousness of Adverse Events

Changes in adverse event intensity or seriousness are recorded on multiple rows in the dataset. An adverse event that changes in intensity or seriousness will contribute to the count of events as a single event.

In summaries of adverse events presented by intensity, the maximum intensity of the adverse event will be used. The maximum intensity is searched for in events with changes, as well as over repeated events based on the preferred term. For TEAEs and causally related TEAEs, the record(s) with the maximum intensity and maximum related intensity within an analysis phase will be flagged in ADaM data with ASEVMAX=Y and ARSEVMAX=Y, respectively. Adverse events for which information on intensity is missing will be classified as *severe*. Adverse events for which information on seriousness is missing will be classified as *serious*.

During the course of an event, information about all changes in intensity are collected (intensity and start date of intensity change). In ADaM data, changes in intensity are included as additional records (rows) to the originally reported adverse event reflecting the way data are collected. For instance, an adverse event that changes from mild to moderate will have two records, one with intensity mild and one with intensity moderate. Start date for the first intensity will be the start date for the originally reported event. The stop date for the last intensity will be the stop date for the originally reported event, and for the preceding intensities the stop date will be set to the date of reported change in intensity minus 1, or the date of reported change if a change occurring on the same day as the originally reported event, or if there is more than one change on a day.

If an adverse event changes from non-serious to serious, in addition to the originally reported adverse event start date, the start date for the seriousness is reported. However, the event is only reported as serious in the adverse event eCRF. In ADaM data, adverse events that change

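### The default in SAP 24.3 for adverse events with an incomplete start date overrides a known phase, so some open-label events on Lu AF82422 in former placebo patients are tabulated as double-blind placebo events

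*SAP*

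**What the plan says.** SAP 24.3 sorts treatment-emergent events into phases by date. The open-label (OLE) phase takes "TEAEs with date of onset or worsening of intensity/seriousness after first dose of IMP in the OLE period (Visit 1E", up to the final follow-up visit. The section then closes with a default: "If the start date is missing/incomplete and not eligible for imputation, the TEAE will be assigned to the DOUBLE BLIND phase".

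What counts as eligible is governed by SAP 24.4.4: "No imputation of start/stop dates will be done, except in the case of adverse events which change in intensity/seriousness". For events that do change, SAP 24.5.2 says: "Start date for the first intensity will be the start date for the originally reported event".

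SAP 24.4.4 also decides which incompletely dated events are treatment-emergent. If the start date is missing or incomplete and "the stop date is prior to the first dose of IMP, the adverse event will be classified as a pre-treatment adverse event". Otherwise: "In all other cases of an adverse event with a missing/incomplete start and/or stop date, the adverse event will be classified as a TEAE".

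On treatment and reporting, Protocol 7.4 says "In the optional OLE period, all patients will receive Lu AF82422", and Protocol 17.10.1 says "Adverse events, sorted by system organ class and preferred term, will be summarized by period and treatment group".

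**The concern.** The default in 24.3 pays no attention to what is already known about timing. Suppose a former placebo patient has an event whose month and year are recorded and lie entirely after the first open-label dose, with only the day missing. The patient was on Lu AF82422 when it began. The event meets the substance of the OLE rule in 24.3, yet the closing sentence of the same section puts it in the double-blind phase, and the by-group table then shows it under placebo.

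Two tables are affected. The double-blind table is the randomised comparison of adverse events, and its placebo column would hold events that began on active drug. The open-label table, where first exposure of former placebo patients is seen, would lose them.

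**Working it through.** The documents give no figure that depends on this rule, so there is nothing to reproduce. The check is a reading of the sections together, followed by the size per affected patient.

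**Step 1: does the qualifier in 24.3 exclude anything?** SAP 24.4.4 rules out imputation of adverse-event dates except where intensity or seriousness changes. In that exception, SAP 24.5.2 carries the reported start date into the first record and derives dates only for the later records. No rule fills in an incomplete onset date, so every such date is ineligible and the default applies to it.

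**Step 2: which routes avoid the default?** There are two. An event with a stop date before first dose becomes pre-treatment (24.4.4). A dated worsening after the first open-label dose creates a record that also goes to OLE (24.3). Neither moves the onset of an open-label event with an incomplete start date out of the double-blind phase.

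**Step 3: is this the SAP's general practice for partial dates?** No. SAP 24.4.3 (medication) and 24.4.5 (diagnosis and symptom onset) complete partial dates from the parts that are known. Adverse events are handled differently.

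**Step 4: consequence by randomised arm.**
- Placebo: phase wrong and drug wrong. The event leaves the open-label table and enters the double-blind placebo column.
- Active: phase wrong, drug right. The event enters the double-blind active column.

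**Step 5: size per affected patient.** Planned arm sizes are 20 placebo and 40 active (Protocol synopsis). If the patient is not already counted for that term:
- placebo incidence rises by 1/20 = 5.0 percentage points;
- active incidence rises by 1/40 = 2.5 percentage points.

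SAP 16.1.6 plans a table of preferred terms with incidence of at least 5%. One misplaced patient reaches 5% in the placebo arm, if the cut-off is applied by arm.

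**Step 6: effect on the comparison.** Let p_A and p_P be the true double-blind incidences, and let misplaced events add the same amount d to both. The difference is (p_A + d) − (p_P + d) = p_A − p_P, which is unchanged. The ratio (p_A + d)/(p_P + d) is closer to 1 than p_A/p_P. So with equal rates the relative comparison is diluted and the risk difference is not shifted.

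**Step 7: how likely is at least one affected former placebo patient?** The rate of incomplete dates is not in the documents, so these rates are assumptions. With n entrants to the OLE and a chance q per entrant of at least one such event, P = 1 − (1 − q)^n.

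| q (assumed) | n = 12 | n = 20 |
|---|---|---|
| 2% | 22% | 33% |
| 5% | 46% | 64% |
| 10% | 72% | 88% |

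**The case against.** The strongest objection is that the effect may be negligible. Protocol 11.3 requires start and stop dates, events are asked about at every visit, and SAP section 19 provides for blinded data review throughout. Few start dates may stay incomplete. SAP section 5 also locks the double-blind database once no patient remains in that period, so the first report can contain only open-label events already recorded by patients who entered the OLE early. Affected events would be visible in the listings. All of this stands. It limits the size but does not make the rule correct, and by-period tables produced after the OLE are fully exposed.

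Three stronger readings are tempting, and the documents do not support them.
- A reader might infer that every incompletely dated event goes to double-blind. The pre-treatment and dated-worsening routes in Step 2 are exceptions.
- A reader might infer that the rule hides harm. It adds open-label events to both columns. A directional shift in the risk difference would need different rates of incompletely dated open-label events by original arm, and nothing in the documents indicates that.
- A reader might set phase lengths side by side and infer that most incompletely dated events are misplaced. With same-day OLE entry, the SAP's 48-week OLE with follow-up to Week 64 gives 64/(64 + 72) = 47% to 64/(64 + 48) = 57% of the weeks. The protocol's 96-week OLE plus 16 weeks gives 112/(112 + 72) = 61% to 112/(112 + 48) = 70%. These are shares of time under a constant-rate assumption, applied to an unknown count, and they ignore the double-blind lock. They do not measure error in the randomised table.

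**Conclusion.** The point holds as a flaw in a stated rule. SAP 24.3 places some events in a phase that their recorded month and year contradict, and it conflicts with its own definition of the OLE phase. The treatment attribution is wrong only for patients randomised to placebo. For those randomised to active, only the phase is wrong.

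The size is up to 5 percentage points of placebo incidence, or 2.5 points of active incidence, per affected patient for a given term. This assumes the planned arms of 20 and 40 and a patient not already counted. With similar rates in both arms the relative comparison is diluted; no bias in a particular direction is shown. How often this happens cannot be determined from the documents and may be seldom. The change is worth making because it is cheap and the present rule discards usable information.

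**What to change.** Amend SAP 24.3, and 16.1.4 for consistency, with one sequence applied identically in both randomised arms:

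1. Compare the known part of the start date, and the stop date, with the date of the first open-label dose. Assign OLE or double-blind when this settles the phase.
2. If the event had already been reported at a visit before the first open-label dose, assign double-blind.
3. For events that remain ambiguous, keep one common default, flag them in the listing, and add a sensitivity table with them placed in the other phase.

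The default should not differ by arm. Sending unresolved events to OLE only for former placebo patients would remove true double-blind events from one randomised arm and not the other. First reporting at Visit 1E should not by itself assign OLE either, because that visit can fall on the day of the double-blind end-of-treatment visit and the event may have begun before the dose.

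SAP 24.3 and 24.4.4 should also be reconciled on what makes a start date eligible for imputation, or the qualifier deleted.

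The cost is a few lines of SAP text, a change to the analysis-dataset derivation and one extra table. No new data are needed.

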24.4 Handling Missing or Incomplete Dates/Times

24.4.1 IMP Start and Stop Dates

For deriving variables for adverse events and concomitant medication:

- Missing IMP start date will be imputed for enrolled patients by the date of the baseline visit
- Missing IMP stop date will be imputed for enrolled patients by the date of the latest attended visit (scheduled/unscheduled/withdrawal)

For evaluating validity of efficacy assessments:

• Missing IMP stop date will be imputed for enrolled patients by the date of the latest attended visit (scheduled/unscheduled/withdrawal) before the safety follow-up

Exposure will not be calculated for patients with missing IMP start and/or stop dates.

24.4.2 Withdrawal Date

For withdrawn patients with a missing Withdrawal Visit, the date of the last attended visit before safety follow-up will be used in the calculation of time to withdrawal from treatment.

24.4.3 Medication Start and Stop Dates

Concomitant medications with missing start and stop dates will be classified according to the following rulesas determined from the IMP start date. Incomplete dates will be evaluated and compared to IMP start date by imputing the missing information as follows:

- If Day is missing (DD): for start dates, 1 will be used; for end dates, the last day in that respective month, i.e., 28/29/30/31
- If Month is missing (MMM): for start dates: January will be used; for end dates, December will be used
- If Year is missing (YYYY): for start dates: year will be set to the year before IMP start; for end dates, year will be set to the year after last IMP

No duration will be calculated for ongoing medications and for medications with missing/incomplete start date and/or stop date.

24.4.4 Adverse Event Start and Stop Dates

If the start date is missing/incomplete for an adverse event and the stop date is prior to the first dose of IMP, the adverse event will be classified as a pre-treatment adverse event. In all other cases of an adverse event with a missing/incomplete start and/or stop date, the adverse event will be classified as a TEAE. No imputation of start/stop dates will be done, except in the case of adverse events which change in intensity/seriousness. For details on deriving multiple events from change in intensity/seriousness, and corresponding stop- and start dates, see section 24.5.2.

For adverse events ongoing at the end of the study, the date of the last study contact will be used as the stop date for the adverse event in the calculation of duration. For other adverse events with a missing/incomplete start or stop date, the duration will not be calculated.

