Screening/Randomization	Pro	ced	ures	and	d As	ssess	sme	nts																	
Signed informed consent	$\sqrt{}$																								
Demographics (age, sex, race)	1																								
MSA diagnostic criteria: Possible or probable, MSA-P or MSA-C	√																								
MSA History	√																								
MoCA	√	 .																							 
Relevant medical history (for example, psychiatric, neurological)	√																								
Recent and on-going medication	1																								
Height																									
Blood sampling for pregnancy test	1																								
MRI scan for eligibility f	1																								
Inclusion/exclusion criteria																									
Signs and symptoms present at SCR, Randomization and/or BL (before IMP	√	√	√																						
administration; recorded on an Adverse Event Form)																									
Randomization																									
Efficacy Assessments																									
UMSARS	$\sqrt{}$		1									√			1			1			$\sqrt{}$			$\sqrt{}$	
SE-ADL			$\sqrt{}$									V						1						$\sqrt{}$	
COMPASS Select			√																						
COMPASS Select Change	[											$\sqrt{}$						√						$\sqrt{}$	
CGI-S			$\sqrt{}$						$\sqrt{}$			$\sqrt{}$			√			√			√			$\sqrt{}$	
PGI-S									$\sqrt{}$			$\sqrt{}$			$\sqrt{}$									$\sqrt{}$	
OGI-S									√			√			√			√			√			$\sqrt{}$	
Fall diary, daily recording	 	√g	√h				√g		$\sqrt{h}$	[	√g	√h		√g	√h		√g	√h							
FeetMe® (subset) optionali		√j	√k				√j		√k		√j	√k		√j	√k		√j	√k							
PAMSys (subset) optional i	l	√j	√k				√j		$\sqrt{k}$		√j	√k		√j	√k		√j	$\sqrt{k}$					]		

Visit Name	Screening	Randomization	Baseline + IMP	Telephone Visit	IMP	Site Visit	IMP	Telephone Visit	IMP	IMP	IMP	IMP	IMP	IMP	IMP	IMP	IMP	IMP/EoTDBP a	EoTDBP/WD b	$_{ m SFU}^c$					
Visit Number	1	2	3	4	5	6	7	8	9	10	11	12	13	14	15	16	17	18	19	20	21	22	23	24	25
Week d	-6	-2	0	2	4	6	8	10	12	16	20	24	28	32	36	40	44	48	52	56	60	64	68	72	88
Visit Window e (days relative to nominal visit)		± 3	± 3	± 3	± 3	± 3	± 3	± 3	± 3	± 3	± 3	± 3	± 3	± 3	± 3	± 3	± 3	± 3	± 3	± 3	± 3	± 3	± 3	± 3	± 7
MRI scan: vMRI, DTI and ASL measures l,m			1						1			1						1						√n	
CSF sampling o for NfL and t-tau			√															V						√p	ļ
Blood sampling for NfL												$\sqrt{}$			√			V							[
Quality of Life Assessment	s																								

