## 9.4.4 Safety Follow-up Visit 20 Weeks After Last Dose of IMP – Double-blind Period

A Safety Follow-up is conducted to capture new adverse events that occur during the Safety Follow-up Period as well as to follow-up on the outcome of adverse events on-going at the end of the treatment period. In addition, the following will be collected; blood and urine samples for clinical safety laboratory tests, blood sampling for IMP quantification and anti-drug antibodies (ADAs), vital signs, physical and neurological examination, ECG, C-SSRS assessment, concomitant medication and pregnancy test. The Safety Follow-up Visit must be conducted as a visit to the site. The Safety Follow-up Visit is scheduled 20 weeks after the last dose of IMP.

For adverse events that were on-going at the EoTDBP or Withdrawal Visit and that resolved during the Safety Follow-up Period, the stop date must be recorded. For non-serious adverse

events still on-going at the Safety Follow-up Visit, the *On-going Adverse Event* checkbox on the *Adverse Event Form* must be ticked. SAEs must be followed until resolution, or the outcome is known.

For details of assessments to be conducted at the Safety Follow-up Visit see Panel 2.

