16.1.3 Classification of Adverse Events

Adverse events will be classified according to the date of onset (or worsening of intensity/seriousness) of the adverse event and end date as follows:

- *pre-treatment adverse event* an adverse event that starts (or worsens) on or after the date the patient signed the *Informed Consent Form* and prior to the date and time of first dose of IMP
- *treatment-emergent adverse event* (TEAE) an adverse event that starts (or worsens) on or after the date of first dose of IMP

An adverse event is considered causally related to the use of the IMP when the causality assessment by the investigator is probable or possible.

Data handling of change in intensity or seriousness of adverse events is described in section 24.5.2.

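### SAP 24.4.4 lets a missing stop date, or a missing day of onset, turn an adverse event that began before the first dose into a TEAE

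*SAP*

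**What the plan says.** SAP 24.4.4 has a two-step rule for events with missing or incomplete dates. The exception comes first: "If the start date is missing/incomplete for an adverse event and the stop date is prior to the first dose of IMP", the event is pre-treatment. Then comes the default: "In all other cases of an adverse event with a missing/incomplete start and/or stop date, the adverse event will be classified as a TEAE". The section imputes no dates except where intensity or seriousness changes. For events ongoing at the end of the study it substitutes the date of last contact as the stop date, but only to calculate duration.

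SAP 16.1.3 classifies by onset or worsening. A TEAE is "an adverse event that starts (or worsens) on or after the date of first dose of IMP". A pre-treatment event is one that starts or worsens after consent "and prior to the date and time of first dose of IMP". Protocol 17.10.1 likewise defines a TEAE as "an adverse event that starts or increases in intensity during or after administration of first dose of IMP". None of these definitions asks whether the event has stopped.

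SAP 24.3 assigns phases. PRETREAT is for records that are not TEAEs. DOUBLE BLIND needs onset or worsening after the first double-blind dose. A TEAE whose start date is missing or incomplete, and cannot be imputed, goes to DOUBLE BLIND by default.

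On data collection, protocol Panel 2 has the row that begins "Signs and symptoms present at SCR, Randomization and/or BL (before IMP", recorded on an Adverse Event Form. Protocol 9.4.4 has sites tick a checkbox for non-serious "events still on-going at the Safety Follow-up Visit".

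**The concern.** The words *and/or stop* bring the stop date into a classification that should depend on onset or worsening. A known pre-dose start then no longer settles the matter once the stop date is blank. A similar loss occurs with partial start dates: 24.4.4 ignores a known month or year, although the SAP uses partial dates for medications (24.4.3) and for diagnosis and symptom onset (24.4.5).

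What is at stake is the content of the TEAE tables. SAP 16.1.6 summarises TEAEs by preferred term, in a table of terms with at least 5% incidence, and by causality and intensity. Events that predate the drug do not belong there. Protocol 11.1.2 treats causality as not relevant for pre-treatment events, so a reclassified record may have no value for the causality table. SAP section 23, which lists departures from the protocol's analyses, does not mention this one.

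**Working it through.** The plan gives no figure for this rule, so the check is to run every combination of start and stop date through the three SAP sections. Events are assumed not to worsen and to occur before any open-label dose.

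| Start | Stop | 16.1.3 | 24.4.4 | Phase in 24.3 |
|---|---|---|---|---|
| before first dose | before | pre-treatment | not engaged | PRETREAT |
| before first dose | after | pre-treatment | not engaged | PRETREAT |
| before first dose | missing | pre-treatment | **TEAE** | **none fits** |
| after first dose | after | TEAE | not engaged | DOUBLE BLIND |
| after first dose | missing | TEAE | TEAE | DOUBLE BLIND |
| missing/incomplete | before | undetermined | pre-treatment | PRETREAT |
| missing/incomplete | after | undetermined | TEAE | DOUBLE BLIND (default) |
| missing/incomplete | missing | undetermined | TEAE | DOUBLE BLIND (default) |

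One of the eight cells is in direct conflict: known pre-dose start, stop missing. There, 24.4.4 makes the record a TEAE, which bars it from PRETREAT, while its onset date bars it from DOUBLE BLIND.

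The last two rows hide the partial-date case. They are undetermined only when the known part of the start date leaves the order open. Three invented records, all with first dose on 10 May 2022, show the difference:

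1. Onset 20 Apr 2022, stop date missing. 16.1.3: pre-treatment. 24.4.4: TEAE. 24.3: no phase.
2. Onset in Apr 2022 with the day missing, stopped 1 June 2022. The month alone proves pre-dose onset. 24.4.4: TEAE. 24.3: DOUBLE BLIND.
3. Onset 20 Apr 2022, stopped 1 June 2022. 24.4.4 is not engaged. Pre-treatment, correctly.

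Records 2 and 3 can describe the same event; losing the day of onset changes the class.

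**Size, as illustration only.** The documents give no event rates. Let q be the share of patients in each arm with a misclassified pre-dose event, independent of true TEAEs, and suppose these records do reach the tables. Reported incidence is then p + (1 − p)q. With assumed true incidences of 60% and 40%:

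- q = 5%: 0.60 + 0.40 × 0.05 = 62%; 0.40 + 0.60 × 0.05 = 43%; difference 19 points.
- q = 30%: 0.60 + 0.40 × 0.30 = 72%; 0.40 + 0.60 × 0.30 = 58%; difference 14 points.

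The true difference of 20 points shrinks by the factor (1 − q), and both arms are inflated.

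**After the fix.** The cell with a known pre-dose start and missing stop becomes pre-treatment, and so does record 2. Events whose start date is truly uninformative remain TEAEs unless they stopped before dosing.

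**The case against.** The strongest reply is that an ongoing event does not have a missing stop date: a ticked box is recorded information. SAP 24.4.3 (medications) and 24.5.2 (duration by intensity or seriousness) both list ongoing separately from missing or incomplete. Against this, 24.4.4 deals with events ongoing at study end and then turns to *other* events with a missing or incomplete date, which groups the two. The SAP is ambiguous here. A reader might infer that every ongoing pre-treatment event is misclassified; the text does not establish that. The narrower case stands either way: a known pre-dose start with an unknown stop date, for instance after loss to follow-up.

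A second reply is that these records may never reach the double-blind tables. TEAE summaries are by study period, and a complete pre-dose start fits no phase. This stands: for such records, inflation of the tables is undefined, not demonstrated. It does not cover partial start dates, which 24.3 sends to DOUBLE BLIND.

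Third, a reader might expect many chronic MSA symptoms to be swept in. Protocol 11.1.1 points the other way: conditions present before consent are medical history, natural progression of MSA is not reported unless serious, and falls are reported only when serious. What remains is mainly new, non-MSA events arising between consent and first dose.

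Finally, counting events with an unknown start as TEAEs is a usual conservative choice. That is right, and it is not the defect.

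**Conclusion.** The rule as written gives a wrong class in two situations: a known pre-dose start with a missing stop date and no worsening, and a partial start date whose known part is before the first dose when the event did not stop before dosing. The first contradicts SAP 16.1.3 and protocol 17.10.1 and leaves the record without a phase. The second puts the record in the double-blind phase.

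The size is unknown and probably small, given the limits on what is reported as an adverse event. A reader might compare the 6-week pre-dose window with 64 to 88 weeks of later observation and infer 7% to 9% extra TEAEs (6/88 = 6.8%, 6/64 = 9.4%). That needs a constant onset rate and no pre-treatment event ever resolving, and the documents support neither. With 40 and 20 patients, two active or one placebo patient make 5%, so a few records could move a term into the 5% table, but no such count is given.

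The rule is the same in both arms, the safety analyses are descriptive, and no efficacy result is touched. The likely effect is inflated TEAE counts and some dilution of arm differences. The sections should be reconciled before unblinding, because programmers following different ones would classify the same record differently.

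**What to change.** In SAP 24.4.4, delete *and/or stop* and state:

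> Each record is classified by its date of onset or of worsening in intensity/seriousness (see 16.1.3 and 24.5.2). A missing stop date or an ongoing status does not affect classification. If the start date is missing/incomplete, the event is a TEAE unless the known part of the start date, or the stop date, shows that it began or ended before the first dose and it did not worsen on or after first dose.

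The reference to worsening is needed. A rule on start date alone would class an event that began before dosing and worsened on treatment as pre-treatment, which under-counts TEAEs.

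Align 24.3: PRETREAT should take events shown to have begun before dosing without later worsening, and the DOUBLE BLIND default should be limited to TEAEs whose start date remains undetermined.

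The cost is a few sentences in the SAP and a small change to the adverse event derivation. No new data are needed.
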